
In designing a treatment that can be employed by PC-MHI providers, we considered several options but ultimately chose to modify the VA's full length CBT protocol³². First, CBT has the most well-established evidence base of psychotherapies for chronic pain^{31,33} and has therefore been rolled out extensively in VA. Second, a recent trial comparing CBT to another form of therapy for chronic pain, mindfulness-based stress reduction, found that the effect of these treatments is equivalent³⁴, indicating that mindfulness does not offer significant advantages over CBT. Third, six-session CBT for chronic pain groups have been shown to be cost effective for use in non-VA primary care³⁵, suggesting the potential of a briefer version of CBT in the primary care setting. Fourth, our prior work has shown that a clear majority of PC-MHI providers self-report use of CBT techniques as part of their routine practice to address other mental health conditions³⁶⁻³⁹. Nationally, some PCMHI providers play a role in delivering psychoeducational group interventions, or "pain schools", in primary care, yet the availability of these interventions is variable and the content is not standardized. Significantly, their overall effectiveness at improving patient outcomes appears marginal⁴⁰, suggesting that pain schools may be insufficient as the principal approach to addressing the psychosocial aspects of chronic pain. Therefore, a standardized protocol would capitalize on therapeutic elements that have demonstrated effectiveness, match well with the PC-MHI treatment platform, and address a significant concern among primary care patients.

Significance

The long term goal of this research is to promote recovery and psychological wellness among Veterans with chronic pain. The proposed study will advance knowledge in rehabilitation research by providing preliminary data regarding the feasibility and effectiveness of Brief CBT-CP as a front line treatment. More immediately, this pilot study will provide the necessary information to develop a proposal for a full scale effectiveness trial. This intervention has been designed specifically for PC-MHI providers and therefore has clear implications for translation to clinical practice. The potential direct benefit to Veterans includes offering a safe, accessible, evidence-based, non-pharmacological treatment for chronic pain early in the trajectory of VA care.

Research Design and Methods

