Patients will be excluded if chart review indicates either of the following: 1) unstable psychiatric status (e.g., active psychosis, current mania) or 2) major or minor neurocognitive disorder (e.g., dementia). Patients will also be excluded if chart review reveals uncontrolled medical conditions, scheduled/planned surgeries, and medical or other interventions likely to impact pain/functional ratings. Potential participants will not be excluded based on past/current/future use of chiropractic care or physical therapy.

Procedures. As shown in Figure 1, upon completing baseline measures, eligible participants will be randomly assigned to (1) Brief CBT-CP plus TAU or (2) TAU only. Assignment to Brief CBT-CP will be stratified based on degree of pain interference as measured by West Haven-Yale Multidimensional Pain Inventory – Interference (WHYMPI-I)⁵³. Participants will be classified as average interference and below (WHYMPI-I score ≤ 4.4) or as above average interference (WHYMPI-I score >4.4)^{28,53}. All participants will complete a telephone-based follow-up with the study coordinator, who will be blinded to participants' condition, at 8 weeks (post-test) and at 12 weeks (follow-up) from randomization for re-administration of study measures. Participants will be compensated \$40 for the initial assessment and \$30 for each of two follow ups (total \$100 for Aim 1). We will replace dropouts who do not meet minimum treatment completion requirements of attending ≥ 4 sessions. Attending, at minimum, sessions one through four will provide patients with essential education and core CBT self-management skills. Although some dropout is planned, we predict that we will replace only a small number of participants (~3-4) prior to our final 12-week follow-up assessment. This prediction is informed by [name] (Co-I) current clinical trial (IIR I01HX000909) of a brief behavioral intervention for depression conducted at the Buffalo VAMC primary care clinics which used similar methodology. At 90% completion, this study has evidenced only 11.3% participant drop out at 12-week follow-up.

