during follow-up assessment calls. To assess the suitability of our measures of patient outcome measures, we will examine item response rates, including the number of missed responses and multiple responses, and time required for completion. We will also document any questions or comments raised by the participant during measure administration. To assess fidelity of service delivery, the study interventionist will complete an adherence checklist after each session. Checklists map on to each of the six sessions of Brief CBT-CP and will be designed to capture key content and procedures. All intervention sessions will be audio recorded with the participant's permission. The PI will randomly select 25% of the audio recordings for review by [name] (study Co-I) using an adapted version of the CBT-CP Rating Scale⁵⁵. To examine the precise nature of participants' service utilization during the trial, we will conduct a chart review at 12-week follow-up. Chart review will assess participants' engagement in primary medical care (i.e., PACT encounters), PC-MHI encounters, and other VA services to assist with assessing feasibility of TAU only as a control condition and will assess any changes in pain or psychotropic medication initiated since baseline assessment. Aim 1 Measures of patient outcomes. Patient outcome measures will be assessed at baseline, post treatment (eight weeks), and follow-up (12 weeks). Administration of all study measures will take about one hour at each time point.

- West Haven-Yale Multidimensional Pain Inventory Interference (WHYMPI-I). The WHYMPI-I is a validated 9-item subscale that evaluates pain-related interference in daily activities and social and occupational functioning⁵³. It is among the core assessments included in the full-length CBT for Chronic Pain³² and is the primary patient outcome for this trial.
- Brief Pain Inventory Short Form (BPI-SF): The BPI-SF is a psychometrically validated 9-item measure that assesses pain level (current and average), pain related functional impairment, and activity interference. The BPI-SF asks participants to indicate the extent of their pain as well as any interference with various activities and other aspects of life (i.e., mood, relationships) using a scale ranging from 0 (no pain/interference) to 10 (worst pain/complete interference). This measure is included in order to further assess pain outcomes in response to Brief CBT-CP.

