- Working Alliance Inventory Short Form Revised (WAI-SR): The WAI-SR is a 12-item self-report measure that asks participants about their perceptions of their therapist (i.e., my therapist and I respect each other) and the therapeutic services they receive (i.e., what I am doing in therapy gives me new ways of looking at my problem). Participants indicate on a scale from 1 (seldom) to 5 (always) how well each statement describes their own experiences in therapy. This instrument is included in the current protocol in order to examine potential differences in treatment outcomes as a result of the participants' rapport with their study therapist.
- **Demographics Form:** This form requests standard information on patient demographic background, including the following: age, gender, race, living arrangements, marital status, education, and occupation.

Aim 1 Study conditions.

Brief CBT-CP plus TAU: Brief CBT-CP is a manualized protocol that includes six, 30-minute sessions over the course of 6 weeks. Brief CBT-CP session outlines and patient handouts are included in the appendix. Session one focuses on foundational pain education and the development of treatment goals. Session two emphasizes balanced engagement in physical activity and pleasurable events. Session three emphasizes skills training for easily implemented relaxation techniques. Sessions four and five focus on recognizing and modifying unhelpful thoughts that negatively impact pain. Session six focuses on relapse prevention and independent implementation of CBT-CP skills following treatment. Brief CBT-CP will be delivered by a masters-level interventionist either at the Buffalo VA Medical Center or by telephone depending on the preference of the participant. The interventionist will be trained by Drs. [name] (Co-I) and [name] (PI) in how to apply the protocol. Training will include at least 20 hours of didactic explanations of the principles of each intervention, role play and feedback exercises, discussion of case examples, and skill rehearsal. Audio recordings of sessions will be reviewed by [name]. If the interventionist has deviated significantly from the protocol based on CBT-CP Rating Scale⁵⁵ scores, or related measures, s/he will be provided with corrective feedback and assigned training cases until deficiencies are corrected.

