All in-person research sessions will be conducted in private rooms. For telephone calls, researchers will conduct calls in private rooms, review the purpose of the telephone call, request that Veterans be in a location where they feel comfortable discussing those topics (e.g., scheduling, conducting phone assessments, etc.), and reschedule if Veterans are not in an appropriate location at that time. Multiple procedures will be in place to minimize psychological risk including: (1) participants will be reminded that they can choose not to answer any question that they are uncomfortable with, (2) participants will be reminded that they can choose to withdraw from the study at any time, and (3) licensed psychologists will be available to speak with Veterans who report significant distress during any study procedure. To further minimize risks for participants, it will be emphasized throughout the protocol that participation is voluntary and may be discontinued at any time. Participants will be told that stopping their participation will not adversely affect the care they receive at the VA. They will also be notified that they can choose to be referred to behavioral health services as an alternative to their participation in the research. Participants will be informed that study personnel may choose to discontinue their participation at any time if it is deemed inappropriate for the participant (e.g., participant evidences psychotic symptoms). Limits of confidentiality and importance of Veterans' safety will be outlined. During the informed consent process, participants will be notified that should they report anything that threatens their safety or the safety of someone else, [name] will contact them to discuss this concern. In cases of imminent risk and child/elder abuse, mandated reporting and referrals to appropriate mental health services will take place. We will monitor participants for adverse events at each study contact. Any adverse event will be reported to the local IRB.

In the unlikely event that an individual becomes acutely distressed, or evidence risk of harm to self or others, he/ she will be evaluated and referred for emergency mental health services. Study staff will have a specific protocol to follow regarding emergency care (suicide assessment protocol) and will have the support of Drs. [name] and [name], licensed psychologists with significant prior experience in addressing patient safety concerns.

References

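### Adverse events are sought at each study contact, which gives Brief CBT-CP about eight scheduled contacts after randomisation and TAU two, so any by-arm event count would be open to unequal ascertainment

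*Combined protocol and SAP*

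**What the plan says.** The section Protection Against Risk gives the collection and reporting rules together: "We will monitor participants for adverse events at each study contact. Any adverse event will be reported to the local IRB." It gives no definition of an adverse event, no standard question, no look-back period and no end date for collection.

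The number of contacts depends on the arm:

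- **Brief CBT-CP plus TAU** (Aim 1 Study conditions): "six, 30-minute sessions over the course of 6 weeks", delivered by the study interventionist.
- **TAU only** (same section): no behavioural sessions from the study.
- **Both arms** (Procedures): "All participants will complete a telephone-based follow-up with the study coordinator", at 8 and 12 weeks from randomisation. The coordinator is to be blinded to condition.

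Three other provisions bear on the point. Procedures requires at least two telephone attempts and a letter when a participant misses a scheduled contact. The patient outcome measures, including the PHQ-9 and GAD-7, are given to both arms at 8 and 12 weeks. Measures of feasibility plans a chart review at 12 weeks, with no restriction by arm: "Chart review will assess participants' engagement in primary medical care (i.e., PACT encounters), PC-MHI encounters, and other VA services". It also covers changes in pain and psychotropic medication, but adverse events are not among its stated purposes.

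The Aim 1 Analysis plan contains feasibility descriptives and exploratory patient outcomes. It contains no adverse-event table and no safety comparison.

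**The concern.** Looking for harm at every contact is sound participant protection. It is not an arm-neutral way of counting events when one arm is seen far more often by design. A minor event in week 2 can be mentioned at the next session by a Brief CBT-CP participant. A TAU participant has no scheduled contact until week 8, by which time the event may be forgotten or thought not worth raising. The extra contacts are also with someone who knows the assignment, whereas the shared calls are made by a blinded coordinator.

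Two things are at stake. The pilot exists to test trial processes for a full-scale effectiveness trial, and adverse-event collection is one of those processes; an unequal method carried forward would distort a comparison that matters more. Within the pilot, all events go to the IRB. With 15 participants per arm, a list weighted towards Brief CBT-CP by detection alone could give a wrong impression even without formal analysis.

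Separately, a participant who cannot be reached has no named source of adverse-event data. This falls hardest on TAU, where the two calls are the only scheduled contacts after baseline.

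**Working it through.** The plan states no adverse-event rate, contact count or safety sample size, so there is no figure to reproduce. The check counts contacts from the schedule and then asks what difference in recorded events they could produce.

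**Step 1: scheduled contacts after randomisation.** Inputs are the six sessions (Aim 1 Study conditions), the two follow-up calls, the four-session completion minimum and the reminder call before each appointment (all Procedures), and 15 participants per arm (30 randomised 1:1, Participants).

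| Way of counting | Brief CBT-CP | TAU | Ratio |
|---|---|---|---|
| Sessions plus calls | 6 + 2 = 8 | 2 | 4.0 |
| Four-session completer | 4 + 2 = 6 | 2 | 3.0 |
| Including baseline | 9 | 3 | 3.0 |
| Including a reminder call for each appointment | 16 | 4 | 4.0 |

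The first row gives 15 × 8 = 120 contacts against 15 × 2 = 30. With weekly sessions, the longest gap between scheduled contacts is 4 weeks in Brief CBT-CP (week 8 to 12) and 8 weeks in TAU (randomisation to week 8).

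**Step 2: share of events recorded.** The following are assumptions, not plan content: equal true event rates; onset uniform over 12 weeks; sessions at weeks 1 to 6 and calls at weeks 8 and 12, all attended; and a chance of being reported at the next contact that halves every h weeks. With k = ln 2 / h, an interval of L weeks ending in a contact yields (1 − exp(−kL)) / k weeks' worth of recorded events. The share recorded is the sum over intervals divided by 12. Brief CBT-CP has six intervals of 1 week, one of 2 and one of 4; TAU has one of 8 and one of 4.

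Worked case, h = 2, k = 0.3466:

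- Interval yields: L = 1 gives 0.845; L = 2 gives 1.443; L = 4 gives 2.164; L = 8 gives 2.705.
- Brief CBT-CP: (6 × 0.845 + 1.443 + 2.164) / 12 = 0.723.
- TAU: (2.705 + 2.164) / 12 = 0.406.
- Ratio: 0.723 / 0.406 = 1.78.

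| Recall half-life | Brief CBT-CP | TAU | Ratio | Ratio if only four sessions attended |
|---|---|---|---|---|
| 2 weeks | 72% | 41% | 1.78 | 1.58 |
| 4 weeks | 84% | 60% | 1.40 | 1.31 |
| 8 weeks | 91% | 76% | 1.20 | 1.16 |
| 26 weeks | 97% | 92% | 1.06 | 1.05 |
| Perfect recall | 100% | 100% | 1.00 | 1.00 |

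**Step 3: participants not reached.** Someone who misses both calls may still have had up to six session contacts in Brief CBT-CP, but has no completed scheduled contact after baseline in TAU, apart from any reminder calls. Procedures cites 11.3% drop-out at 12 weeks in a different trial at the same clinics. Used purely as an illustration, 0.113 × 30 = 3.4 participants, or 0.113 × 15 = 1.7 per arm. This is not a rate of failed adverse-event collection in this trial.

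**Step 4: comparison on shared calls.** If arms are compared on events learned of at the two calls, with the same question, the schedule is 2 against 2 contacts and the structural difference disappears. Recall loss remains, but applies to both arms alike.

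**The case against.** The strongest reply is that the plan makes no safety comparison. The monitoring rule sits in a participant-protection section, sends events to the IRB, and suits that purpose. This stands: a reader might infer that the trial's by-arm safety counts are biased, but no such counts are planned. The point concerns what the collected data could support.

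Second, unequal contact does not by itself produce unequal counts. Both arms have the two calls, and with good recall or a clear look-back question the difference shrinks to nothing. This also stands. A reader might infer that Brief CBT-CP is bound to show more events, or that detection scales with the fourfold difference in contacts; neither follows. The absolute effect may be small too: with an assumed three true events per arm and a 4-week half-life, about 2.5 would be recorded against 1.8.

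Third, one might infer that anyone who misses a call goes unmonitored. The documents do not support that. Missed contacts are followed up, reasons for drop-out are to be sought during follow-up calls (so those who leave therapy are still expected to be called), and the chart review may bring emergency visits or admissions to light under its heading of other VA services. What survives is that no source is designated for adverse events in a participant who is never reached.

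Fourth, the harm the plan names most directly is psychological distress, and the PHQ-9 and GAD-7 are administered to both arms on the same schedule with follow-up by a blinded coordinator. That protects much of the most relevant domain, but not other kinds of event.

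Finally, the Significance section's phrase "offering a safe, accessible, evidence-based, non-pharmacological treatment for chronic pain" describes what the treatment might offer Veterans. It is not a safety claim that this pilot sets out to test.

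**Conclusion.** The concern holds in a limited form. Adverse-event detection is structurally unequal, at 8 against 2 scheduled contacts after randomisation, with six of the eight held by someone who knows the arm. Any by-arm count from this collection would be open to differential ascertainment, most likely in the direction of more events under Brief CBT-CP.

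The direction is predictable; the size is not. The range from 1.0 to about 1.8 rests entirely on the assumed recall model, on weekly sessions and on full attendance, because the documents give neither a look-back period nor a standard question. A participant who is never reached has no named adverse-event source.

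For a 30-person feasibility pilot with no planned safety comparison, severity is minor to moderate. The main reason to act is that the method may be carried into the larger trial.

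**What to change.** 1. Keep monitoring and IRB reporting at every contact, unchanged.
2. At the 8- and 12-week calls, ask one identically worded adverse-event question in both arms, covering the time since randomisation (first call) or since the last call (second call).
3. Name the existing 12-week chart review as an adverse-event source, with a field for items such as emergency visits, admissions and safety events. Complete it for every randomised participant, including those not reached by telephone.
4. If events are summarised by arm, report all of them by source. Draw the between-arm comparison from the two common sources, and show session-detected events alongside. They should not be left out: Potential Risks names discomfort with the intervention as a possible harm, and such events would tend to surface in sessions.

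The cost is one extra question at each of two existing calls and one extra field in an existing chart review, a few minutes per participant. Recall loss remains in the call data, but equally in both arms.
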